24.0 APPENDIX B: DATA AND SAFETY MONITORING PLAN (DSMP)

Data and Safety Monitoring Plan Template

1.0 BRIEF STUDY OVERVIEW

In this project, we will develop and beta-test the Facebook intervention. We formed a study-specific CAC to review intervention content, measures, and recruitment messaging and provide advice on all study activities. Members are health care providers, AIAN community partners, and AIAN women, with some being former opioid users.

2.0 OVERSIGHT OF CLINICAL RESPONSIBILITIES

A. Site Lead Investigator

The site's LI (LI) is responsible for study oversight, including ensuring human research subject protection by designating appropriately qualified, trained research staff and medical clinicians to assess, report, and monitor adverse events.

All adverse events (AEs) occurring during the course of the study will be collected, documented, and reported by the investigator or sub-investigators according to the Protocol.

The occurrence of AEs and serious adverse events (SAEs) will be assessed in the follow-up survey via self-report questions on trips to the Emergency Department, hospitalizations, and overdoses. Serious adverse events will be followed until considered resolved or stable.

B. Safety Reporting

The LI (LI) may appoint a Site Medical Clinician (MD, DO, NP, or PA) or utilize the Mayo Clinic on-call physician for this study, who will review or provide consultation for each Adverse Event (AE) and Serious Adverse Event (SAE) as needed. These reviews will include an assessment of the possible relatedness of the event to the study intervention or other study procedures. The Site Medical Clinician will also provide advice for decisions to exclude, refer, or withdraw participants as required. A site clinical psychologist or psychiatrist may also review AEs and SAEs as needed. The study staff will determine which safety events require expedited reporting to NIDA and regulatory authorities. This will include events that are serious, related, and unexpected. The study staff will be trained to monitor for and report AEs and SAEs, and participants will report AEs and SAEs at the follow-up visit.

The study site has established practices for managing medical and psychiatric emergencies, and the study staff will continue to utilize these procedures. Treatment providers at the site will be responsible for monitoring participants for possible clinical deterioration or other problems, and for implementing appropriate courses of action.

Voluntary Regulatory Reporting in non-IND Trials:

For non-IND trials, if an event meets expedited reporting criteria (serious, related and unexpected) the Safety Monitor/Medical Monitor or designee will voluntarily report to FDA/Regulatory Authorities using the MedWatch Form 3500 or similar.

C. Data and Safety Monitoring

We will use the FDA definition of adverse events (AEs) and serious adverse events (SAEs). The FDA guidelines for anticipated or unanticipated SAEs will be followed. Regarding monitoring participant safety, any SAE, whether or not it is related to the study intervention, will be reported to the IRBs and NIDA. The Program Coordinator, study staff and intervention moderators located at the site, will evaluate for the presence of both SAEs and AEs at each scheduled contact, regardless of whether conducted in person, via telephone, or online. Drs. [name] and/or [name] and will meet with the research staff via teleconference on a bi-weekly basis to review any new or continuing SAEs and AEs.

D. Quality Assurance (QA) Monitoring

The Manual of Operations will be developed by the Program Coordinator. We will use the same coordination, communication and quality control procedures successfully utilized in our previous work. Study staff will be trained using the SOP and the quality control of the data (accuracy and completeness of data) will be monitored on a monthly basis by the study statistician. The quality of the data (data checks) including missing data and presence and frequency of outliers. The site study team will meet weekly discuss progress and problem solve issues related to recruitment and data collection.

The intervention moderators will be trained as detailed in the Phase 2 procedures. A “refresher” training will occur every three months after the initial training. [name], a consultant trainer, will review moderator-participant discussions every week after the Facebook group has been initiated and provide additional feedback to the moderators every two weeks.

The research team will develop written intervention moderator guidelines for how often the moderator should log in, check-in and respond to comments/postings and other expectations for moderator engagement. A potential concern about using social media for health interventions is that user postings may be of poor quality, for example, inconsistent with clinical practice guidelines or involve inappropriate or illegal activities. When participants enter the study, they will be informed about the policies for posting content and that any inappropriate postings will be removed. The moderator will be trained to handle inappropriate or misinformation, and to direct information content toward evidence-based information exchange and social support. All study staff and volunteers will be required to complete and pass the CITI HIPPA/confidentiality course prior to any subject contact.

E. Management of Risks to Participants

Confidentiality

Confidentiality of participant records will be secured by use of study codes for identifying participants on CRFs, and secure storage of any documents that have participant identifiers on site, as well as secure computing procedures for entering and transferring electronic data. The documents or logs linking the study codes with the study participant on site will be kept locked/securely stored separately from the study files and records. No identifying information will be disclosed in reports, publications, or presentations.

Information That Meets Reporting Requirements

The consent form will specifically state the types of information that are required for reporting and that the information will be reported as required. These include suspected or known sexual or physical abuse of a child or elders or threatened violence to self and/or others.

Participant Protection

The site's study clinician or other designated and qualified individual will evaluate all pertinent screening and baseline assessments prior to participant enrollment to ensure that the participant is eligible and safe to enter the study. AEs will be assessed and documented at each study visit. Individuals who experience an AE that compromises safe participation in a study will be discontinued from further intervention and provided referrals for other treatment or to specialized care. Study personnel will request that the participant complete an end-of-intervention visit to assure safety and to document end-of-intervention outcomes.

A detailed plan is in place for clinical management of psychiatric or medical problems that might arise. The study staff will monitor any reports or observations of medical problems or psychiatric symptoms based on the K6 scale in participants which is administered at the baseline and follow-up visits. In the event of such an occurrence, they will set into motion procedures for referral of the participant for mental health assessment and care. Study staff will contact the LI or one of the study clinicians for further assessment of the participant's symptoms and current clinical care. Subjects who are patients at Mayo Clinic will be referred for additional mental health assessment and treatment at Mayo Clinic. However, study participants will not likely be Mayo Clinic patients. Thus, in the event of an emergency (e.g., suicidal plan), staff physicians will be consulted to refer the subject to Hennepin Healthcare or a local tribal medical facility in Minneapolis or St. Paul for further assessment and clinical care. Also, individuals who report suicidal intent or other severe psychiatric or medical problems will be referred to Hennepin Healthcare or a local tribal medical facility and followed throughout the study period. Drs. [name], [name], and/or [name] (licensed clinical psychologist, board certified psychiatrist, and a physician) or the Mayo Clinic on-call site physician will be consulted by study staff as needed. Continued participation with the study will be voluntary and in cooperation with the health care professional treating the subject's psychiatric or medical condition.

Study Specific Risks

Participants may feel inconvenienced by completing study assessments and providing urine samples. They may feel uncomfortable in front of the study staff if their urine is positive for any

drugs. Facebook posts and comments may cause emotional discomfort for the participants depending on what other members and moderators post. There is a chance that the participants experience withdrawal symptoms as they continue to abstain from opioids, but this risk is minimal because they would have already abstained from illicit opioid use for at least 30 days at screening. What symptoms may occur are expected to be mild and may consist of nausea, abdominal discomfort, muscle and joint pain, perspiration, runny nose and eyes, yawning, irritability, and anxiety. Since this FB intervention is not anonymous, confidentiality of health information could be compromised. However, the intervention group moderators will emphasize that all information shared in the group should stay in the group, and any samples and identifiers outside of the intervention will be destroyed.

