8.4 Participant Exclusion Criteria

AIAN potential participants in Phases 1 and 3 meeting any of the exclusion criteria listed below will be excluded from study participation. Interested party participants in Phase 1 will only fail the screening if they meet the second exclusion criterion.

- (1) Self-reports current suicidality
- (2) Inability or unwillingness of participant to provide verbal consent (Phase 1) or written informed consent (Phase 3)
- (3) (Phase 3 only) Was a participant in Phase 1

Pregnant women, lactating women, or women who plan to become pregnant will not be excluded because the treatment being evaluated is a behavioral intervention and does not involve medication or risk to the fetus.

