10.3.7. Discontinuation of Study Intervention

If the subject never engages in the Facebook group or discontinues from the intervention but not from the study, remaining study procedures will be completed as indicated by the study protocol.

If a clinically significant finding is identified (including, but not limited to changes on the K6 scale from baseline) after enrollment, the investigator or qualified designee will determine if any change in participant management is needed. Any new clinically relevant finding will be reported as an adverse event (AE) if it meets the definition specified in Appendix A of the protocol. A plan is in place for clinical management of depression and other psychiatric symptoms or medical problems. The study staff will refer participants to the appropriate on-call physician or behavioral health clinician at the appropriate medical facility. The study staff will have a list of contacts as participant issues or concerns arise that need medical or psychiatric attention, or when other types of referral or assistance are needed. Individuals who report suicidal intent or other severe psychiatric symptoms or medical problems will be referred for treatment and followed throughout the study period. Continued participation with the study will be voluntary and in cooperation with the health care professional treating the subject's psychiatric or medical condition.

The study staff will be trained by [name], licensed clinical psychologist, and Dr. [REDACTED] [REDACTED], Mayo Clinic Board Certified Psychiatrist, to observe and monitor depression and psychiatric symptoms. They will be available to consult with the study staff as needed.

In the event a participant withdraws from the study or the LI decides to discontinue a participant due to an SAE, the participant will be monitored by the LI via ongoing status assessment until:

- (1) Resolution is reached (i.e., the problem requiring treatment has resolved or stabilized with no further changes expected)
- (2) The SAE is determined to be clearly unrelated to the study intervention
- (3) The SAE results in death.

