10.3.9. Phase 3 Table of Assessments

Concept	Assessment	Visit
Participant eligibility measures	Screening survey	Time 1
	Opioid Use Disorder diagnosis based on the DSM-5 checklist (American Psychiatric Association, 2013)	Time 1
	Timeline Follow-Back interview (Sobell et al., 1988) to assess opioid and other substance use in past 30 days	Time 1
	Current suicidality based on 3 items from the Concise Health Risk Tracking—Self Report (CHRT-SR) Suicidal Behavior Evaluation (Trivedi et al., 2011)	Time 1
	Urine drug screen [REDACTED] [REDACTED] [REDACTED] [REDACTED] (https://cliawaived.com/fentanyl-rapid-tests-20.html)	Time 1
Baseline sociodemographics	Baseline survey using PhenX Toolkit items (Hamilton et al., 2011)	Time 1
User experience measures	Social Media Usability scale (Lund, 2001) and open-ended questions	Time 2
Opioid use outcome measures	Urine drug screen [REDACTED] [REDACTED] [REDACTED] [REDACTED]	Time 2

	(https://cliawaived.com/fentanyl-rapid-tests-20.html)	
	Timeline Follow-Back interview (Sobell et al., 1988) to assess opioid and other substance use in past 30 days or since study enrollment	Time 2
MOUD retention	Timeline Follow-Back interview (Sobell et al., 1988) MOUD use in past 30 days or since study enrollment	Time 2
Psychiatric symptom measure	K6 scale (Kessler et al., 2002)	Time 1, Time 2
Spirituality measure	Items from World Health Organization's Quality of Life Spirituality, Religion, and Personal Beliefs measure (WHOQOL SRPB Group, 2006)	Time 1, Time 2

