11.2. K6 Scale

In Phase 3, we will use the K6 scale (Kessler et al., 2002) at baseline and follow-up assessments. Included in the PhenX toolkit (Hamilton et al., 2011), the K6 is a screening measure that assesses psychological distress including depressive and anxiety symptoms over the past month. The K6 measures distress with six questions (e.g., “How often did you feel nervous?” “How often did you feel hopeless?”) scored on a five-point Likert scale ranging from 0=none of the time to 4=all of the time. Total scores can range from 0 to 24. The K6 scale is a widely used indicator of nonspecific psychological distress and is highly correlated with mental illness. Moreover, studies have shown that having a score of 13 or greater on the K6 is a strong indicator of the presence of a DSM

diagnosable psychiatric disorder with considerable disability (Furukawa et al., 2003; Kessler et al., 2003). The K6 has been validated in general population samples (Forman-Hoffman et al., 2014) and among AIAN adults specifically (Mitchell & Beans, 2011).

If a K6 score of ≥ 13 is prevalent at baseline or follow-up, or if a substantial increase in scores from baseline is noted at follow-up, the LI or one of the study clinicians will follow-up with the participant for further assessment and initiate referral for additional mental health assessment and care as described in the DSMP.

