11.3. Assessment of Suicidality at Screening

In the Screening for study eligibility for Phase 1 (AIAN women only) and Phase 3, the study staff will use three items from the Concise Health Risk Tracking-Self Report (CHRT-SR) Suicidal Behavior Evaluation (CHRT-SR) (Trivedi et al., 2011), a self-report assessment of suicidality and related thoughts and behaviors. The scale assesses suicidality quickly and easily in a manner consistent with the Columbia Classification Algorithm of Suicide Assessment (C-CASA) (Posner et al, 2007). The CHRT-SR will assess high risk for suicidality by a positive response ("Agree" or "Strongly Agree") on the last three questions (thoughts of, thoughts of how, and/or a specific plan to commit suicide) and prompt a clinician assessment for suicide risk before ending the screening visit. A study clinician will complete the Concise Health Risk Tracking – Clinician Rated (CHRT-CR) (Trivedi et al, 2011) to aid in his or her assessment of symptoms and he/she will initiate referral for additional mental health assessment and care as described in the DSMP.

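### After screening no instrument asks about suicidality, although the plan provides for acting on it; the only structured psychiatric measure afterwards is the K6 at follow-up

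*Combined protocol and SAP*

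**What the plan says.** **At entry.** Section 8.4 lists "Self-reports current suicidality" as the first exclusion criterion. Section 11.3 says how it is measured: "In the Screening for study eligibility for Phase 1 (AIAN women only) and Phase 3, the study staff will use three items" from the CHRT-SR, covering thoughts of suicide, thoughts of how, and a specific plan. The Phase 3 assessment table in 10.3.9 places "Current suicidality based on 3 items from the Concise Health Risk Tracking—Self Report (CHRT-SR) Suicidal Behavior Evaluation" among the eligibility measures, at Time 1 and nowhere else.

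**After entry.** Section 10.3.8 itemizes the follow-up: usability and open-ended questions, the Timeline Follow-Back, other treatments, the spirituality items, the K6, a urine screen, and safety questions on emergency visits, hospitalizations and overdoses. No suicidality item is named. On the K6, section 11.2 states: "The K6 scale is a widely used indicator of nonspecific psychological distress and is highly correlated with mental illness". Section 18.19.1 uses the K6 score to define reportable clinical deterioration.

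**What the plan intends to do.** Section 10.3.7: "Individuals who report suicidal intent or other severe psychiatric symptoms or medical problems will be referred for treatment and followed throughout the study period". Appendix B, section 2.0 E, has parallel wording and gives a suicidal plan as an example of an emergency. It has staff monitor reports or observations of "medical problems or psychiatric symptoms based on the K6 scale in participants", the scale being one "which is administered at the baseline and follow-up visits". Section 12 lists becoming a threat to oneself among the reasons for ending participation.

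**The concern.** The plan treats suicidality as important enough to exclude on at entry and to act on afterwards, yet it measures it only at entry. The scale carried into follow-up is described as covering depressive and anxiety symptoms and general distress, with no suicidality content mentioned.

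Two things are at stake. For the individual woman, recognition depends on her raising the matter or on someone noticing. For the report, the safety analysis in 17.3.4 tabulates adverse events that were recorded. If no one is asked, an absence of suicidality in that table cannot be told apart from an absence of questions. The protocol itself says, in 4.3.1 and in the study-specific risks of Appendix B, that group posts may cause emotional discomfort, and in 6.1 that the findings are meant to support a pilot RCT.

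**Working it through.** No sample size or error rate bears on this point. The check sets the assessment schedule beside the safety text, then looks at how far the K6 could stand in.

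**Step 1. Count of scheduled suicidality assessments in Phase 3.** Screening (10.3.1, 10.3.9, 11.3): 1. During the 30-day group: 0. Follow-up (10.3.8, 10.3.9): 0. Total after enrollment: 0.

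**Step 2. Every channel that operates after entry.**

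| Where | Channel | Stated to ask about suicidality? |
|---|---|---|
| 10.3.8, 11.2 | K6 at follow-up | No; described as nonspecific distress |
| 10.3.8, 11.1 | Questions on emergency visits, hospitalizations, overdoses | No |
| 11.1 | Spontaneous reports to staff; reports from secondary contacts if a woman cannot be reached | No; unprompted |
| Appendix A | Psychiatric as well as medical adverse events assessed from consent | No; general |
| Appendix B, 2.0 C | Staff and moderators evaluate adverse events at each scheduled contact, including online | No; general |
| 10.3.7 | Staff trained to observe depression and psychiatric symptoms | No; observation |
| 10.3.5 | Moderators check in every 1-2 days | No; the listed tasks are interaction, guideline adherence and removing posts |

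The K6 is thus not the only channel, but it is the only structured psychiatric one. Observation of the group also cannot reach a woman who never engages, a case that 10.3.7 and 17.3.2.2 both foresee.

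**Step 3. Could the K6 substitute?** Inputs from 11.2: six items, each scored 0-4, past-month recall, action at 13 or more or at a substantial increase of no stated size.

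- Maximum score: 6 × 4 = 24, which reproduces the protocol's range.
- Three items at the maximum and three at zero: 3 × 4 = 12, below 13. Marked distress on half the items need not reach the cutoff.

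**Step 4. Which group days does the follow-up K6 cover?** Inputs: a 30-day group (10.3.5) and a six-week, or 42-day, visit window (10.3.8). Assumptions: the window runs forward from the end of the group, and a month is 30 days. A visit on day d recalls days d − 30 to d, so the overlap with the group is max(0, 60 − d) days for d from 30 to 72 (30 + 42 = 72).

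- d = 30: 60 − 30 = 30 of 30 days.
- d = 51: 60 − 51 = 9 of 30 days.
- d = 60 or later: 0 of 30 days.

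Even as a measure of general distress, the follow-up K6 may cover little or none of the group period, depending on when the visit falls.

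**The case against.** The strongest reply is that the plan is broader than the K6. A reader might infer that psychiatric safety after enrollment is monitored with that scale alone, or that a woman scoring 12 or less with no rise meets no stated trigger. The documents support neither reading. Psychiatric adverse events are in scope from consent, staff and moderators evaluate adverse events at every scheduled contact, and clinicians review them every two weeks. Section 10.3.7 makes K6 change only one example of a clinically significant finding, and the sentence in Appendix B covers reports and observations. Suicidality noticed by any of these routes could be referred and would enter the adverse event summary.

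It can also be said that the plan promises to act on suicidal intent that is reported, not to look for it systematically, so there is no outright contradiction. That is right: this is a gap between what is measured and what is to be acted on, not a broken commitment.

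Nor is suicidality found later necessarily new. The exclusion rests on self-report, so it may have been present and undisclosed at screening.

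What survives is narrower. None of the other routes is stated to ask about suicidality. They widen the chance of noticing it but do not supply a measurement with a known denominator.

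A practical objection is that follow-up may be by phone whereas Phase 3 screening asks these items in person. It carries little weight, because section 10.1.4 already has the same items given by phone or video in Phase 1. The objection that consent describes the questions as part of screening (10.3.2) does stand, and is counted as a cost.

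**Conclusion.** The point holds in this form: after screening no instrument asks about suicidality, and the one structured psychiatric measure that follows is the K6 at follow-up. Its size is one scheduled suicidality assessment before enrollment and none after. Detection of suicidal thoughts after entry rests on disclosure, observation or general adverse event questioning, while 10.3.7 and Appendix B provide for acting on intent or a plan. In a sample of 10, one unrecognized case is 1/10 = 10% of the women; that shows how coarse the sample is and says nothing about how often such a case would arise.

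The conclusion assumes that 10.3.8 and 10.3.9 list the follow-up content in full; the survey form itself is not in the documents. The recall calculation rests on the assumptions stated with it, and the main conclusion does not depend on it. This is an inexpensive improvement to a safety measurement and does not undermine the study's development and feasibility aims.

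**What to change.** 1. In 10.3.8, add the same three CHRT-SR items to the Follow-up Survey, and in 10.3.9 mark them for Time 1 and Time 2.
2. In 17.3.4, report the number of women with any positive item at follow-up, together with the number asked. State that this describes suicidality at the follow-up visit and not throughout the 30-day group; thoughts that arose and resolved earlier would still be missed.
3. Reconcile 10.3.7 and Appendix B, section 2.0 E, with 10.3.8, 10.3.9 and 11.3, so that the protocol says what response applies to a positive item after enrollment. That response is for the sponsor and its clinicians to settle; none is proposed here.

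If the sponsor keeps the present schedule, the protocol and the report should say that suicidality is not systematically assessed after entry.

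The cost is three existing items on a survey that staff already administer, sensitive questions asked once more, and a small consent and IRB amendment because 10.3.2 presents these questions as part of screening.
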